12.5.5.1 Timed 25-Foot Walk (T25FW)

A decrease in average time to complete the two trials will show an improvement.

The difference between treatment arms in the change from baseline to D21 in average 25-foot walk time (as defined in [Section 10.17](#)) will be analyzed using the same LME model for crossover data as the one used for the primary analysis of the primary efficacy endpoint (as described in [Section 12.5.2.1.8](#)). As a sensitivity analysis, the same analysis will be repeated using non-imputed average 25-foot walk times (as defined in [Section 10.17](#)).

If model diagnostics suggests that the residuals are not normally distributed a non-parametric analysis will be conducted.

A $\geq 20\%$ reduction from baseline to D21 of in average time (as described in [Section 10.17](#)) will be analyzed using a logistic regression applied to crossover design using a GEE (as described in [Section 12.5.2.3.2](#)).

A histogram presenting LS means change from baseline estimates along with their corresponding 95% CI will be provided by treatment arm.

Descriptive statistics for the average T25FW values change from baseline and percentage change from baseline by treatment arm will be provided; as well as a by-patient listing presenting observed and derived variables.

12.5.5.2 11-point Numerical Rating Scale Score (NRS-spasticity score)

The 11-point NRS spasticity scale is composed of 11 items ranging from 0 (no spasticity) to 10 (maximal spasticity) to assess the overall spasticity in patients with MS during the last 24 hours.

The difference between treatment arms in the 7-day average NRS spasticity score over the last 7 day preceding D21 of each period (as defined in [Section 10.18](#)) will be analyzed using a linear mixed model for crossover data using the SAS® GLIMMIX procedure with an identity link function and a normal distribution. The 7-day average NRS spasticity D21 score will be included as the dependent variable. Hence, each patient will contribute two measurements to the model, one for each period of the study.

The preferred model will include period level treatment arm, treatment period, and treatment sequence as fixed effects. Unstructured (UN) covariance structure will be used to model the repeated 7-day average NRS spasticity scores. The denominator degrees of freedom will be calculated according to Kenward-Roger method (e.g., KR2, 2009 version).

In case of non-convergence of the preferred model or memory space issue the, the compound symmetry covariance structure will be applied to the preferred model described above.

This model will provide the LS mean estimates for each treatment arm, along with the SEs and 95% CIs as well as, the LS mean treatment difference between nabiximols and placebo in NRS spasticity score along with the SE, 95% CI and the nominal p-value for treatment arm comparison.

In addition, this model will present the LSmeans estimates along with 95% CIs for each treatment period and treatment sequence, as well as the difference between treatment periods and treatment sequences and nominal p-values for treatment sequence and treatment period comparison.

The 7-day average NRS spasticity scores will be summarized at baseline, Day 15 and D21 per treatment arm and, per treatment period and overall.

Mean \pm SD 7-day average NRS spasticity score will be plotted per treatment arm by 7-day period.

Furthermore, a histogram presenting LS means estimates and corresponding 95% CIs will be plotted per treatment arm.

A by-patient listing presenting 7-day average NRS spasticity score along with the corresponding score per day will be provided.

12.5.5.3 Daily Spasm Count

The 7-day average daily spasm count is derived from spasm counts recorded daily by the patients in the eDiary.

The difference between treatment arms in the average daily spasm count over the last 7 day preceding D21 of each period (as defined in [Section 10.19](#)) will be analyzed using the same approach as the one used to analyze 7-day average NRS-spasticity score (as described in [Section 12.5.5.2](#)).

The 7-day average daily spasm count will be summarized at baseline, Day 15 and D21 per treatment arm and, per treatment period and overall.

Mean \pm SD 7-days average daily spasm will be plotted per treatment arm by 7-day period.

Furthermore, a histogram presenting LS means estimates along with their corresponding 95% CIs will be provided by treatment arm.

A by-patient listing presenting 7-day average daily spasm count along with the corresponding count per day will be provided.

12.5.5.4 The MS Spasticity Scale

The MSSS-88 is a patient self-report measure of the impact of spasticity (muscle stiffness and spasms) in MS. It is composed of 88 items ranging from 1 (not at all bothered) to 4 (extremely bothered).

These items are grouped to derive 8 subscales (as defined in [Section 10.20](#)) within 3 different categories which are composed of: 3 spasticity symptoms (i.e., muscle stiffness, pain and discomfort, muscles spasms), 3 areas of physical functioning (i.e., effects on daily activities, ability to walk, body movement) and 2 areas of psychosocial impact (i.e., emotional health, social functioning).

Difference between treatment arms in total and subdomain scores of the MSSS-88 at the end of the maintenance-dose phase (D21) of each double-blind treatment period will be analyzed using the same approach as the one used to analyze the 7-day average NRS-spasticity score (as described in [Section 12.5.5.2](#)).

A histogram presenting LS means estimates along with their corresponding 95% CIs will be provided for respectively for the 8 subscale scores and for the total score.

The 88 items as well as subscales and total scores will be summarized by treatment arm.

A by-patient listing presenting the total score along with the 8 subscales scores will be provided

12.6 Pharmacokinetics

Plasma concentrations will be obtained for THC and its relevant metabolites (11-hydroxy- Δ 9-tetrahydrocannabinol and 11-carboxy- Δ 9-tetrahydrocannabinol) and CBD and its relevant metabolites (7-hydroxy-cannabidiol and 7-carboxy-cannabidiol) at distinct time points (as described in Table 8.1-2) on Day 1, Day 15 and D21 of each treatment period.

Concentration data will be summarized per treatment arm, treatment period and overall, by analysis day (as defined in [Table 10.1-1](#)) and hours (see Table 8.1-2) since last dose for post-baseline samples of THC and its relevant metabolites and of CBD and its relevant metabolites. Concentrations that are below the limit of quantitation (BLQ) will be excluded from the computation of descriptive statistics but the number of patients presenting a concentration below the limit of quantification will be presented at each time point. The number of observations, mean, standard deviation, geometric mean, geometric standard deviation, coefficient of variation (%), median, minimum, maximum values will be displayed

Individual data will be presented in listing.

If concentration data show that sufficient systemic exposure for THC or one or more of the metabolites is available, relevant PK parameters may be calculated using a population PK model. In that case, PK results will be presented in a stand-alone report. This report might also include a post hoc PK/PD analysis on the basis of PK and pharmacodynamics (PD) data collected in the study.

12.7 Safety Analyses

The safety analyses will be conducted during the 51-day on-treatment safety period (as described in [Section 10.1](#)) by actual treatment arm. As appropriate, the safety analyses will also be conducted during the follow-up period (as described in [Section 10.1](#)) by treatment sequence. All the safety analyses will be conducted using the Safety Analysis Set.

Some analyses of adverse events and laboratory parameters will assess the potential impact of the study drug among the subgroups presented in Table 12.7-1.

Table 12.7-1 Subgroups applied to Safety Analysis

Group Variables	Subgroup	Comments
Sex	Male Female	
Age group	≤ 18 , > 18 and ≤ 45 ≥ 46 to ≤ 65 > 65	According to patient's distribution within age, age group may be differently defined Detailed derivation is given in Section 10.10
Race	White Black or African American Asian American Indian or Alaska Native Native Hawaiian or Other Pacific Islander Other	According to patient's distribution within race some races may be grouped together
Prior cannabis use	Yes No	If it appears that one patient has missing prior cannabis use information, the missing category will be added for AE summary
Number of current antispasticity medication	0 1 2 ≥ 3	

Patient mean number of daily sprays	≤ 6 sprays, > 6 sprays and ≤ 12 sprays, > 12 sprays.	This is referring to “Patient means number of daily spray” taken during the maintenance phase (derivation as described in Section 10.8.2)
-------------------------------------	--	--

12.7.1 Adverse Events

Adverse events (AEs) will be coded using MedDRA 24.0 or higher according to the version in use at time of database lock. All safety analyses of AEs will be performed by actual treatment arm and reported using the Safety Analysis Set. An AE will be considered a TEAE if it first occurs or worsens in severity or seriousness after the first dose of IMP intake and before the last dose date + 15 days.

All AEs will be classified during the pre-treatment period, the 51-day safety on-treatment period or during the follow-up period as follows:

- Events that occurred before first IMP intake without worsening or becoming serious after the first IMP dose are classified as **pre-treatment AEs**;
- Events that occurred or worsens between first IMP dose and 14 days after IMP last dose are classified as on-treatment AE and are defined as **treatment-emergent AEs** (TEAEs);
 - TEAE occurring during 21-day on-treatment safety Period 1 will be considered emergent to actual treatment received during Period 1 (as defined in [Section 10.1.1](#)).
 - TEAE occurring during 21-day on-treatment safety Period 2 will be considered emergent to actual treatment received during Period 2 (as defined in [Section 10.1.1](#)).
- Events occurring more than 15 days after last dose are classified as **follow-up AEs**.

Consequently, TEAEs will be summarized by treatment arm using the actual treatment received at each given period. Any adverse event occurring during the wash-out period will be linked to the actual treatment arm defined for Period 1, whereas any AEs occurring after last IMP dose will be linked to the actual arm defined at time of permanent study drug discontinuation.

The following events will not be identified as AEs in this study:

- Medical or surgical procedures (e.g., surgery, endoscopy, tooth extraction, etc.). The condition (the “triggering event”) that leads to the procedure are adverse events and will be reported as such.
- Pre-existing conditions present or detected prior to the first dose of study drug that do not worsen during the study.

Counting rules

For incidence reporting, if a patient reported more than one AE that was coded to the same preferred term/system organ class within a given treatment arm, the patient will be counted only once for that specific preferred term/system organ class by treatment arm and the rules defined below will be applied.

For TEAEs presented by action taken on study drug, the worst action taken among the events with same SOC/PT emergent to the same treatment arm will be selected for each patient. If action taken is missing for a TEAE, the action taken “drug withdrawn” will be assigned considering the AE leads to permanent IMP discontinuation. The imputed values for action taken will be used for incidence summaries, while the actual values will be used in data listings.

For TEAEs presented by severity, the worst severity among the events with same SOC/PT emergent to the same treatment arm will be selected for each patient. If the severity is missing for a TEAE, then a severity of “Severe” will be assigned. The imputed values for severity assessment will be used for incidence summaries, while the actual values will be used in data listings.

For TEAEs presented by relationship to study drug, the relationship to study drug, as assigned by the investigator, for each event during the clinical trial will be presented for each patient. If the relationship to

investigational product is missing for a TEAE, a causality of “Related” will be assigned. The imputed values for relationship assessment will be used for incidence summaries, while the actual values will be presented in data listings.

For TEAEs presented by categories for time of first onset of AE, if the AE start date is missing, it will be imputed as specified in Table 10.21-1 for AE analysis or summary but actual values will be presented in data listing.

Summary of Adverse Events

For the purpose of inclusion in TEAE tables, incomplete AE onset and end dates will be imputed as specified in [Table 10.21-1](#). No duration will be calculated for adverse events with incomplete start-or stop dates, or for ongoing adverse events.

For summary by SOC and PT the denominator to derive the percentage will be the number of patients at risk in the treatment arm.

For subgroup analysis by SOC and PT the denominator to calculate the percentage will be the number of patients at risk in the treatment arm and in the category of the analyzed subgroup.

For summary by SOC and PT and category of time to first onset of AE the denominator to derive the percentage will be the number of patients at risk in the treatment arm in each time interval category.

For summary by SOC and PT and category of duration of AE the denominator to derive the percentage will be the number of patients in the corresponding treatment arm having experienced a TEAE corresponding to the SOC or PT being summarized.

The number of patients at risk in the treatment arm is defined as the number of patients having taken at least 1 spray of respectively nabiximols or placebo in the actual treatment arm (as defined in [Section 9.3.1](#)) linked to either the 21-day safety period 1 or the 21-day safety period 2 (as defined in [Section 10.1.1](#)).

All summary by SOC and PT will be sorted by descending frequency of nabiximols for SOC and by descending frequency of nabiximols for PT within SOC.

Listing of Adverse Events

All AEs, SAEs, AEs leading to study drug discontinuation, AE with outcome of death; AE of special interest will be listed.

The listings will include Subject ID, actual treatment received, SOC, preferred term, investigator term, start and stop date of the AE, whether or not the AE was treatment emergent, duration, frequency, severity, relatedness, action taken, outcome, and seriousness of the AE. Imputed start or stop dates will not be displayed in listings of AEs. These listings will be sorted by treatment sequence, subject ID and onset of adverse events.

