12 ADVERSE EVENT REPORTING

12.1 Definitions

12.1.1 Adverse Event

For the purposes of this trial, an AE is defined as follows:

Any new unfavorable/unintended signs/symptoms (including abnormal laboratory findings when relevant) or diagnosis or worsening of a preexisting condition that occurs following Screening (Visit 1) and at any point up to the posttreatment Safety Follow-up Visit (Visit 10), which may or may not be considered to be related to the IMP. Any event that is the result of a trial procedure must be recorded as an AE.

Surgical/investigational procedures are not AEs. The medical reason for the procedure is the AE. Elective hospitalizations for pretrial existing conditions or elective procedures are not AEs. An exception may be if the patient has an AE during hospitalization that prolongs his or her scheduled hospital stay, in which case it would be considered a SAE (refer to [Section 12.2](#)).

If reporting a fatal event, the SAE term should be the underlying cause of the death (e.g., disease or medical condition leading to death).

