12.3 Reporting Procedures for Serious Adverse Events

All SAEs occurring during the trial must be reported to GW with any other supporting information and recorded in the AE section of the eCRF. Any ongoing SAEs should be followed up until resolution wherever possible. For all deaths, the working diagnosis or cause of death as stated on a death certificate, available autopsy reports, and relevant medical reports should be sent to GW promptly.

All SAEs must be recorded in the eCRF within 24 hours of discovery or notification of the event. The GW Pharmacovigilance Department (PWD) will be automatically notified that an SAE has been recorded. Any additional information required for a case (follow-up or corrections to the original case) will be requested by GW PVD through eCRF queries.

The investigator is not obliged to actively monitor for any new SAEs that occurred after the last formal Safety Follow-up Visit (Visit 10). However, if the investigator becomes aware of any deaths or a new IMP-related SAE occurring within 28 days of the final dose of IMP, these should be reported to the GW PVD.

Any other problem discovered after Visit 10 that is deemed to be an unexpected safety issue and is likely to have an impact on patients who have taken part in the trial must be treated as an SAE and reported to the GW PVD. Such posttrial SAEs do not need to be

recorded on the patient's eCRF if editing rights to the eCRF have been removed due to final trial database lock. GW PVD may request safety follow-up information after the final trial visit in order to investigate a potential safety issue.

Contact details for the GW PVD are provided at the front of the site files for all trial site and upon completion of the GW SAE report form.

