13.6.1 Evaluable Period

The evaluable period starts on the day of randomization. The end of the evaluable period is defined as the Safety Follow-up Visit (Visit 10).

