13.6.6.2 Adverse Events

AEs will be coded according to the Medical Dictionary for Regulatory Activities dictionary.

A TEAE is one that started, or worsened in severity or seriousness, following the first dose of IMP.

Descriptive presentations of TEAEs will be given by PT and SOC for the Safety Analysis Set. The number of patients reporting at least 1 TEAE will be provided.

The following summaries will be produced at a minimum:

- All-causality TEAEs
- Treatment-related TEAEs
- All-causality TEAEs by maximal severity
- All-causality serious TEAEs
- Treatment-related serious TEAEs
- TEAEs reported as leading to permanent cessation of IMP
- Fatal TEAEs

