10.0 Conventions and Derivations

10.1 Study Period, Reference Day, Study Day, Analysis Day and Visit Window

10.1.1 Study Periods

For each patient, there will be a screening period, an evaluable period composed of a treatment period 1, a washout period, and a treatment period 2, and a safety follow-up period.

The Screening period starts on the day of the informed consent signature and ends on Day 1 (as defined on in [Section 10.1.2](#)) before 1st IMP intake.

The evaluable period starts on the day of randomization and ends the day of the safety follow-up visit.

- The **51-day efficacy period** which starts on the first day of IMP administration and ends at the end of treatment date.
 - This period will be composed of:
 - The **21-day on-treatment efficacy Period 1** which starts the day of first IMP intake during Period 1 and ends the earliest between end of Period 1 D21 date and permanent end of treatment date;
 - The on-treatment **wash-out period** which begins the day following the end of the 21-day on-treatment efficacy Period 1 and ends the day before the beginning of the 21-day on-treatment efficacy Period 2;
 - The **21-days on-treatment efficacy Period 2** which starts the day of IRT call for Period 2 and ends on the end of treatment date. This period is only defined for patients exposed to IMP during Period 2.
 - It will be used for efficacy analyses using the Full Analysis Set.
- The **51-day safety period** which starts on the first day of IMP administration and ends at the end of treatment date (+ x days).
 - This period will be composed of:
 - The **21 day on-treatment Safety Period 1** which starts the day of first IMP intake during Period 1 and ends the earliest between end of the wash out period date, the day before the date of IRT call for Period 2, the day before Visit 6 date and permanent end of treatment date + x days.
 - The **21 day on-treatment Safety Period 2** which starts the earliest between date of Visit 6, day of IRT on treatment safety period call for Period 2 date, and ends on the end of treatment day date + x days.
 - x will be equal to 14 days for Adverse events, 4 days for C-SSRS and 0 days otherwise.
 - it will be used for safety analyses using the Safety Analysis Set (unless otherwise specified).
- The **Follow-up period** which starts the day following the 51-day on-treatment safety period and ends on the end of study date.

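### The SAP closes the TEAE window 14 days after the last dose without declaring the change, so some adverse events collected in patients who stop IMP early miss the by-arm TEAE tables

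*SAP*

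**What the plan says.** Protocol 13.6.6.2 gives the definition: "A TEAE is one that started, or worsened in severity or seriousness, following the first dose of IMP". That sentence has no closing date. The limit comes from elsewhere: Protocol 12.1.1 and 12.6 define and record adverse events up to and including Visit 10, and Protocol 13.6.1 ends the evaluable period at the same visit. Protocol 2.1 lists TEAE frequency among the secondary endpoints.

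The SAP sets a different limit. Section 10.1.1 extends the on-treatment safety period past the end of treatment by x days, where "x will be equal to 14 days for Adverse events, 4 days for C-SSRS and 0 days otherwise". Section 12.7.1 defines a TEAE as one occurring or worsening "after the first dose of IMP intake and before the last dose date + 15 days", and restates this as a classification rule: "Events that occurred or worsens between first IMP dose and 14 days after IMP last dose are classified as on-treatment AE". For the next class it says: "Events occurring more than 15 days after last dose are classified as" follow-up AEs. Section 12.7 analyses the follow-up period by treatment sequence, and only where that is judged appropriate. SAP Table 6.2-1 lists two changes from the protocol, the FAS definition and the added LLMT-10 endpoint. The TEAE window is not among them.

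**The concern.** The SAP narrows the definition of a protocol secondary endpoint, gives no reason and does not declare it. The effect is also uneven. Protocol 10 lists liver enzyme elevations, suicidality and intolerable adverse events among the reasons for ceasing IMP, and says that such patients should remain in the trial. These patients go on being asked about adverse events, but part of what they report can no longer count as treatment-emergent. Patients who take IMP to the end of the period have every collected day counted.

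The tables concerned are those that compare nabiximols with placebo on serious, treatment-related and fatal events. Protocol 14 provides for no data safety monitoring committee, so these end-of-trial tables carry the safety comparison.

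**Working it through.** **Inputs**
- Visit 10 is 7 (+3) days after the later of the last dose and Visit 9 (Protocol 4.1 and 9.1.5).
- A patient who stops IMP early is encouraged to stay to the end of that period, when Visit 9 is held (Protocol 4.1). That is period Day 21, with a window of 2 days either way (Protocol Appendix 1).
- The TEAE window ends 14 days after the last dose (SAP 10.1.1 and 12.7.1).

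**The plan's own date.** A completer has the last dose on Day 51, so Visit 10 = 51 + 7 = Day 58, as the protocol states, or Day 61 at +3. In period terms this is 21 + 7 = Day 28, or Day 31.

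**Completers.** Days from last dose to Visit 10: 58 − 51 = 7, or 61 − 51 = 10. Both are under 14, so no collected day is lost.

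**Washout.** Last Period 1 dose to Visit 6: 31 − 21 = 10 days nominally. The longest gap the visit windows allow is 32 − 19 = 13. Washout events are also covered.

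**Early stoppers who stay.** For a last dose on period Day d:

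collected but uncounted days = max(0, Visit 10 day − d − 14)

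| Last dose, period day | Nominal (Visit 10 on Day 28) | Visit 10 at +3 (Day 31) | Visit 9 at +2 and Visit 10 at +3 (Day 33) |
|---|---|---|---|
| 1 | 28 − 1 − 14 = 13 | 16 | 18 |
| 5 | 28 − 5 − 14 = 9 | 12 | 14 |
| 10 | 28 − 10 − 14 = 4 | 7 | 9 |
| 13 | 1 | 4 | 6 |
| 14 | 0 | 3 | 5 |
| 18 | 0 | 0 | 1 |
| 19 or later | 0 | 0 | 0 |

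The note to SAP Table 10.1-1 expects Visit 10 between Day 25 and Day 31. At Day 25 the first three rows would be 10, 6 and 1.

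**Early stoppers who leave at once.** If Visit 10 follows 7 to 10 days after the last dose, nothing is lost.

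**A concrete case.** After screening, biochemistry, haematology and ECG are scheduled only at the end of each period. Take an adverse event first found and dated at that visit on Day 21. After a last dose on Day 5 it falls 21 − 5 = 16 days later and is a follow-up AE. After a last dose on Day 7 it falls 14 days later and is a TEAE.

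**Day 15.** By the wording of SAP 12.7.1 alone, an event exactly 15 days after the last dose is neither before day 15 nor more than 15 days out. SAP 10.1.1 starts the follow-up period on the day after the safety period ends, which is day 15. The two sections conflict in wording, and 10.1.1 settles where the day belongs.

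**The case against.** The length of the post-dose risk window is partly a matter of judgement, and Protocol 13 leaves analysis detail to the SAP. Counting events weeks after the last spray can dilute a treatment comparison. An adverse event that caused the stop begins by the last dose and is counted under either rule. Staying on after stopping is only encouraged. Late events are not hidden: SAP 12.7.1 lists all adverse events with a treatment-emergent flag, SAP 12.7.1.1 has a by-arm row for related deaths that is not limited to TEAEs, and SAP 12.7.2.1 lists, summarises and narrates deaths recorded as adverse events. All of this stands, and it limits the weight of the point. It does not explain why a secondary endpoint definition changed without an entry in Table 6.2-1, or why collected serious and related events should be left out of the by-arm tables only in patients who stopped.

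A reader might infer three stronger claims that the documents do not support.
- That the protocol window is open-ended. It is not: protocol adverse events end at Visit 10.
- That the SAP drops events to day 28 in every patient, because Protocol 12.3 asks for "any deaths or a new IMP-related SAE occurring within 28 days of the final dose of IMP". That reporting is passive: it applies if the investigator becomes aware of such an event, with no duty to monitor after Visit 10. For completers, days 15 to 28 lie after Visit 10 and so outside the protocol's own adverse event definition.
- That day 15 has no class. SAP 10.1.1 puts it in follow-up.

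**Conclusion.** The concern holds in limited form. The SAP's 14-day limit departs from the protocol's TEAE definition and is not declared. It removes collected adverse events from the by-arm TEAE tables only for patients who stop IMP before about period Day 14 (up to Day 18 with the latest visit windows) and stay to Visit 10. The loss is at most 13 days of collection per patient with nominal visits and 18 with the latest. For completers it is zero.

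The size rests on the visit timing above and on patients staying after they stop. The documents give no figure for how many will stop early and stay. The planned 10% dropout (6 of 52) is a different event and does not supply one. The number of affected adverse events is therefore unknown and probably small. What is at stake is a complete and even-handed set of serious, treatment-related and fatal tables, not the efficacy conclusion.

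**What to change.** In SAP 10.1.1 and 12.7.1, run the TEAE window to Visit 10, at least for the serious, treatment-related and fatal tables. No new attribution rule is needed: SAP 12.7.1 already links adverse events after the last dose to the arm at permanent discontinuation.

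If 14 days is kept for the general TEAE tables:
- declare it in Table 6.2-1 with a reason;
- show follow-up AEs by last treatment received as well as by sequence;
- in SAP 12.7.1, start the follow-up class at more than 14 days after the last dose, to agree with 10.1.1.

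Passive reports received after Visit 10, up to 28 days, should stay in listings and narratives and not be added to the TEAE tables.

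The cost is SAP wording and one date rule in the adverse event dataset. The drawback is that a few late, unrelated events may be counted to the last treatment received.
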